5.4.7. Corticosteroid Taper (LN Cohort Only)

For the LN cohort, the percentage of participants receiving $\leq 7.5 \text{ mg/day}$ will be summarized at Week 14, Week 26, and Week 50 by treatment group by calculating the point estimate and 2-sided 95% CI, based on exact confidence limits using the Clopper-Pearson method.

5.4.8. Renal Flare (LN Cohort Only)

For the LN cohort, renal flare is determined in the opinion of the Investigator in addition to the criteria outlined below and will be recorded on the Renal Flare eCRF:

- For participants who achieve CRR, a renal flare is the reproducible recurrence of proteinuria $\geq 1 \text{ g/g}$.

- For all other participants, a renal flare is either of the following:
 - Reproducible increase of serum creatinine $> 25\%$ higher than baseline or above the upper limit of normal, plus any 1 of the following:
 - Reproducible proteinuria $\geq 75\%$ higher than baseline
 - Worsening active urinary sediment compared to baseline as defined by an increase of ≥ 5 RBCs/high power field or new RBC casts (based on local laboratory results from at least 2 samples)
 - Kidney biopsy newly conducted since the biopsy used for eligibility demonstrating LN Class III or IV activity
 - Reproducible doubling of the UPCR from a 24-hour urine collection compared with the lowest previous value obtained after the first dose of study intervention.

Reproducibility of proteinuria requires that the proteinuria based on a UPCR from a morning spot urine collection is confirmed by UPCR calculated on a 24-hour urine collection obtained within a 2-week period.

Reproducibility of serum creatinine requires 2 blood tests within a 2-week period.

The percentage of participants meeting the criteria for protocol-defined renal flare through Week 50 will be summarized by treatment group by calculating the point estimate and 2-sided 95% CI, based on exact confidence limits using the Clopper-Pearson method.

5.4.9. Extrarenal SLE Flare (LN Cohort Only)

The Systemic Lupus Erythematosus Disease Activity Index Safety of Estrogen in Lupus Erythematosus National Assessment (SELENA) Modification (SLEDAI-2K) tool assesses disease activity across 24 disease descriptors, with a total score ranging from 0 to 105. For the LN cohort, 18 extrarenal disease descriptors of the SLEDAI-2K assessment will be used for the determination of extrarenal SLE flare. An extrarenal SLE flare is defined as an increase in SLEDAI-2K ≥ 4 points that is not accounted for by the renal disease descriptors of proteinuria, hematuria, urinary cellular casts, and hypocomplementemia or an increase in anti-double-stranded DNA (anti-dsDNA) antibody level. Participants who meet the criteria for extrarenal SLE flare may receive additional standard-of-care therapy, if considered clinically appropriate by the Investigator. If additional standard-of-care therapy is administered, the event is considered a severe extrarenal SLE flare. All instances are recorded on the Extrarenal SLE Flare eCRF.

The trajectory of SLEDAI-2K score (excluding renal disease descriptors) over time will be summarized by treatment group and visually presented by plotting the mean values at each time point by treatment group.

The percentage of participants meeting the criteria for protocol-defined extrarenal SLE flare and severe extrarenal SLE flare through Week 50 will be summarized by treatment group by calculating the point estimate and 2-sided 95% CI, based on exact confidence limits using the Clopper-Pearson method.

5.4.10. Suboptimal Response (LN Cohort Only)

For the LN cohort, suboptimal response is determined in the opinion of the Investigator in addition to the criteria outlined below after the Week 26 visit:

- Reproducible proteinuria $\leq 25\%$ decreased compared to baseline

Reproducibility of proteinuria requires that the proteinuria based on a UPCR from a morning spot urine collection is confirmed by a central laboratory UPCR calculated on a 24-hour urine collection obtained within a 2-week period.

The percentage of participants meeting the criteria for suboptimal response through Week 50 will be summarized by treatment group by calculating the point estimate and 2-sided 95% CI, based on exact confidence limits using the Clopper-Pearson method.

5.4.11. Treatment Failure (LN Cohort Only)

For the LN cohort, treatment failure is defined as receipt of additional standard-of-care therapy at any time up to Week 26 or Week 50 for protocol-defined renal flare, severe extrarenal SLE flare, or suboptimal response as recorded on the Rescue Therapy eCRF.

Increase in corticosteroids for extrarenal SLE flare not meeting the protocol definition of severe extrarenal SLE flare, renal flare not meeting protocol definition for renal flare, lack of response not meeting the protocol definition for suboptimal response, other medical conditions or surgery limited to ≤ 14 days duration are **not** included in treatment failure.

The percentage of participants meeting the criteria for treatment failure through Week 50 will be summarized by treatment group by calculating the point estimate and 2-sided 95% CI, based on exact confidence limits using the Clopper-Pearson method.

5.4.12. Serum Albumin (LN Cohort Only)

Serum albumin will be summarized at baseline and each postbaseline time point by treatment group using descriptive statistics for the observed value as well as the change from baseline.

There will be no imputation for missing data or data collected on or after the receipt of additional standard-of-care therapy (for LN cohort) or treatment discontinuation.

The trajectory of serum albumin over time will be visually presented by plotting the mean values at each time point by treatment group.

5.4.13. Partial Remission (IgAN Cohort Only)

For the IgAN cohort, Partial Remission is defined as mean proteinuria < 1 g/day based on 2 valid 24-hour urine collections obtained within 2 weeks prior to the study visit (Week 26 or Week 50).

Participants who discontinue treatment prior to the endpoint assessment will be considered nonresponders.

The percentage of participants meeting the criteria for partial remission will be summarized at Week 26 and Week 50 by treatment group by calculating the point estimate and 2-sided 95% CI, based on exact confidence limits using the Clopper-Pearson method.

A bar chart will also be provided displaying the proportion of participants meeting the criteria for partial remission at Week 26 and Week 50 by treatment group.

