1.1. Objectives and Endpoints

Objectives	Endpoints
Primary (both cohorts)	
To evaluate the efficacy of ravulizumab compared with placebo to reduce proteinuria in adult participants with LN or IgAN	Percentage change in proteinuria from baseline to Week 26 (based on 24-hour urine collection[s] at each time point)
Secondary (both cohorts)	
To evaluate the efficacy of ravulizumab compared with placebo to improve measures of kidney function in adult participants with LN or IgAN	Percentage change in proteinuria from baseline to Week 50 (based on 24-hour urine collection[s] at each time point)
	Percentage of participants with > 30% and > 50% reduction in proteinuria at Week 26 and Week 50 compared to baseline (based on 24-hour urine collection[s] at each time point)
	Change from baseline in estimated glomerular filtration rate (eGFR) at Week 26 and Week 50
	Absolute values and change from baseline in serum C3 and C4 concentrations at Week 26 and Week 50

Objectives	Endpoints
Secondary (LN cohort only)	
To evaluate the efficacy of ravulizumab compared with placebo to improve measures of kidney function in adult participants with LN	Percentage of participants meeting the criteria for complete renal response (CRR) at Week 26 and Week 50
	Percentage of participants meeting the criteria for partial renal response (PRR) at Week 26 and Week 50
	Time to urine protein-to-creatinine ratio (UPCR) $\leq 0.5 \text{ g/g}$ as measured by spot urine sample
	Percentage of participants achieving corticosteroid taper to 7.5 mg/day at Weeks 14, 26, and 50
	Percentage of participants with renal flare through Week 50
	Percentage of participants with extrarenal systemic lupus erythematosus (SLE) flare through Week 50
	Percentage of participants with treatment failure through Week 50
	Percentage of participants with suboptimal response through Week 50
	Absolute values and change from baseline in serum albumin at Week 26 and Week 50
Secondary (IgAN cohort only)	
To evaluate the efficacy of ravulizumab compared with placebo on measures of kidney function in adult participants with IgAN	Percentage of participants meeting the criteria for partial remission at Week 26 and Week 50
Pharmacokinetic (PK)/pharmacodynamic (PD)/immunogenicity (both cohorts)	
To characterize the PK/PD of ravulizumab in adult participants with LN or IgAN	Absolute values and change from baseline in total C5 and free C5 concentrations over time

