3. SAMPLE SIZE DETERMINATION

This study plans to enroll 60 participants in both the IgAN and LN cohorts in a 2:1 ratio to ravulizumab and placebo for a total of 120 participants.

In March 2018, a National Kidney Foundation-sponsored workshop on surrogate endpoints for clinical studies in early stages of chronic kidney disease proposed that a 20% to 30% reduction in the geometric mean of albuminuria or proteinuria was likely to be necessary to ensure a significant treatment effect on the clinical outcome ([Levey, 2020](#)).

Individual patient data from relevant studies in IgAN was previously used to estimate variability and expected changes in proteinuria for patients treated with placebo in addition to background standard-of-care treatment ([Fellstrom, 2017](#)). Based on these data, the geometric mean (GM) of the ratio of 26-week to baseline proteinuria values is assumed to be 0.85 (ie, a 15% reduction in proteinuria) for the placebo treatment group. In order to target at least a 30% relative treatment effect (ie, 1 minus geometric mean ratio [GMR] of ravulizumab to placebo at Week 26), the GM of the ratio of 26-week to baseline is assumed to be 0.55 (ie, a 45% reduction in proteinuria) for the ravulizumab treatment group.

Expected changes in proteinuria and associated variability were not available on the log-scale for patients with LN; however, 2 studies of patients with LN who were treated with mycophenolate mofetil (MMF) showed mean proteinuria values of approximately 4.0 g/day at baseline and approximately 2.0 g/day at Week 24 ([Appel, 2009](#); [Ginzler, 2005](#)). The GM of the ratio of 26-week to baseline proteinuria values is assumed to be 0.60 (ie, a 40% reduction in proteinuria) for the placebo treatment group. In order to target at least a 30% relative treatment effect, the GM of the ratio of 26-week to baseline proteinuria values is assumed to be 0.40 (ie, a 60% reduction in proteinuria) for the ravulizumab treatment group.

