Sample size calculations are based on a 1-sided, 2-sample t-test of log-transformed proteinuria values. The log change from baseline in proteinuria is calculated as $\log(0.85)$ and $\log(0.55)$ for the placebo and ravulizumab treatment groups, respectively, for the IgAN cohort and as $\log(0.60)$ and $\log(0.40)$ for the placebo and ravulizumab treatment groups, respectively, for the LN cohort. A common standard deviation (SD) of log change is assumed to be 0.60 ([Fellstrom, 2017](#)). Under these assumptions and an anticipated 10% drop out rate, a sample size of 60 participants (40 participants randomized to ravulizumab, 20 participants randomized to placebo) will provide approximately 80% power to detect a treatment difference with a 1-sided significance level of 0.05 in each cohort.

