Secondary (key continuous endpoints)	Ravulizumab or placebo	Full Analysis Set	Percentage change from baseline to Week 50 in proteinuria (both cohorts) Change from baseline in eGFR at Week 26 and Week 50 (both cohorts)	Data on or after receipt of additional standard-of-care therapy (LN cohort only) will be imputed using the value collected at the time of renal flare or severe extrarenal SLE flare (or suboptimal after Week 26, if applicable) Data on or after treatment discontinuation will be assumed missing and handled in the MMRM as MAR	Mean of the variable in each treatment group

Table 1: Estimands

Estimand	Treatment	Population	Variable	Handling of IE	Summary Measure
Secondary (key binary endpoints)	Ravulizumab or placebo	Full Analysis Set	
Percentage of participants with > 30% and > 50% reduction in proteinuria at Week 26 and Week 50 compared to baseline (both cohorts)
 
Percentage of participants meeting the criteria for CRR at Week 26 and Week 50 (LN cohort only)
 
Percentage of participants meeting the criteria for PRR at Week 26 and Week 50 (LN cohort only)
 
Percentage of participants meeting the criteria for Partial Remission at Week 26 and Week 50 (IgAN cohort only)
	
Participants who receive additional standard-of-care therapy (LN cohort only) or discontinue treatment are assigned as nonresponders
	Proportion of the variable in each treatment group

Abbreviations: CRR = complete renal response; eGFR = estimated glomerular filtration rate; IE = intercurrent events; LN = lupus nephritis; MAR = missing-at-random; MMRM = mixed effect model for repeated measures; PK = pharmacokinetics; PRR = partial renal response

The secondary estimands for all other secondary endpoints are similar to above except the intercurrent events will be ignored and all data occurring on or after the intercurrent event will be analyzed as observed.

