5.4.4. Complete Renal Response (LN Cohort Only)

For the LN cohort, CRR is defined as meeting all 3 of the following criteria:

- A decrease in mean UPCR to ≤ 0.5 g/g based on two 24-hour urine collections obtained within 2 weeks prior to the study visit (Week 26 or Week 50).
- $eGFR > 60$ mL/min/1.73 m² or no eGFR reduction $\geq 20\%$ from the baseline value based on the mean of 2 values. The first eGFR value must be obtained within 2 weeks prior to the study visit (Week 26 or Week 50), and the second eGFR value will be obtained on the study visit (Week 26 or Week 50).
- No treatment failure (as defined in Section 5.4.11).

Participants who receive additional standard-of-care therapy, discontinue treatment prior to the endpoint assessment or study withdrawal will be considered nonresponders.

The percentage of participants meeting the criteria for CRR as well as individual components of CRR will be analyzed using a CMH test accounting for the stratification factor at Week 26 and Week 50 and will be summarized by treatment group by calculating the point estimate and 2-sided 95% CI based on exact confidence limits using the Clopper-Pearson method.

A bar chart will also be provided displaying the proportion of participants meeting the criteria for CRR as well as individual components of CRR at Week 26 and Week 50 by treatment group.

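### No between-arm estimate is planned for IgAN Partial Remission or for the >30% and >50% proteinuria responders, although the objective is a comparison with placebo

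*SAP*

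**What the plan says.** The IgAN-only secondary objective (SAP 1.1) reads "To evaluate the efficacy of ravulizumab compared with placebo on measures of kidney function in adult participants with IgAN". Its single endpoint is Partial Remission, mean proteinuria below 1 g/day at Week 26 and Week 50. Protocol 4.2.2 calls it a key secondary endpoint.

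The analysis in SAP 5.4.13 is: "The percentage of participants meeting the criteria for partial remission will be summarized at Week 26 and Week 50 by treatment group". Each arm gets a point estimate with a two-sided 95% Clopper-Pearson interval, and there is a bar chart. SAP 5.4.1 treats the >30% and >50% reduction endpoints the same way in both cohorts, and protocol 9.4.1.2.1 and 9.4.1.2.3 agree. SAP Table 1 gives the summary measure for the key binary endpoints as "Proportion of the variable in each treatment group".

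For LN complete renal response, by contrast, SAP 5.4.4 says that it "will be analyzed using a CMH test accounting for the stratification factor at Week 26 and Week 50". SAP 5.5.6 plans the same test for overall renal response, which is only exploratory. Neither section adds an effect size.

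SAP 5.4 labels all secondary analyses descriptive, without multiplicity adjustment.

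**The concern.** A comparative objective needs a comparative summary. As written, the Partial Remission table will show two percentages and two separate intervals, and the reader must supply the contrast. The usual shortcut, checking whether the intervals overlap, is a poor and conservative test.

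The endpoint also depends on where participants start. IgAN entry requires at least 1 g/day and response requires less than 1 g/day, so a participant just above the line needs a small fall and one at 3 g/day needs a large one. Baseline proteinuria (1 to 2 versus >2 g/day) is the IgAN randomization stratum. Stratum and log baseline both enter the primary ANCOVA, but neither enters the responder analysis of the same measurement.

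SAP section 1 says the Week 26 analysis serves Phase 3 planning. Planning on a responder endpoint needs the size of the difference and its uncertainty.

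**Working it through.** **1. The plan's own figure.** SAP 3 gives IgAN Week 26/baseline ratios: placebo "is assumed to be 0.85 (ie, a 15% reduction in proteinuria) for the placebo treatment group" and ravulizumab "is assumed to be 0.55 (ie, a 45% reduction in proteinuria) for the ravulizumab treatment group". The SD of log change is 0.60, with 40:20 randomized and 10% dropout, leaving 36:18. The claim is that this "will provide approximately 80% power to detect a treatment difference" "with a 1-sided significance level of 0.05 in each cohort".

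- Difference: ln(0.85/0.55) = 0.4353.
- Standard error: 0.60 × √(1/36 + 1/18) = 0.1732.
- Power: Φ(0.4353/0.1732 − 1.645) = Φ(0.868) = 80.7% (79.8% by noncentral t).

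The figure reproduces, so these inputs can be carried forward. No power is stated for the responder endpoints.

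**2. Which analyses contain an arm contrast.**

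| Endpoint | Between-arm result planned |
|---|---|
| Primary, Week 26 (SAP 5.3.2) | Adjusted geometric mean ratio, 90% CI |
| LN proteinuria, Week 50 (SAP 5.4.1) | Geometric mean ratio, 90% CI |
| LN complete renal response (SAP 5.4.4) | Stratified CMH test |
| LN overall renal response (SAP 5.5.6) | Stratified CMH test |
| >30% and >50% reduction (SAP 5.4.1) | None |
| IgAN Partial Remission (SAP 5.4.13) | None |

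**3. Dependence of Partial Remission on baseline.** If log change is normal and independent of baseline (an assumption), then for baseline b and ratio g, P(Week 26 < 1 g/day) = Φ((−ln b − ln g)/0.60). For b = 1.1 on placebo this is Φ((−0.0953 + 0.1625)/0.60) = Φ(0.112) = 54%.

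| Baseline (g/day) | Placebo | Ravulizumab |
|---|---|---|
| 1.1 | 54% | 80% |
| 1.5 | 34% | 63% |
| 2 | 19% | 44% |
| 3 | 6% | 20% |

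Moving from 1.1 to 3 g/day changes the placebo probability by 48 points. The treatment difference at any one baseline in the table is at most 29 points.

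**4. The relative endpoints.** For a reduction beyond a fixed fraction, b cancels.

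- >30%: Φ((ln 0.70 − ln g)/0.60) = 37% placebo, 66% ravulizumab.
- >50%: Φ((ln 0.50 − ln g)/0.60) = 19% placebo, 44% ravulizumab.

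Under the plan's model neither depends on baseline, so for these endpoints the gap is only the missing contrast and stratification.

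**5. What two separate intervals can hide.** Take an illustrative 20/40 versus 4/20.

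- Clopper-Pearson intervals are 34-66% and 6-44%, which overlap.
- The difference is 50% − 20% = 30 points.
- With Wilson limits 35.2-64.8% and 8.1-41.6%, the Newcombe lower limit is 0.30 − √(0.148² + 0.216²) = 0.04. The upper limit is 0.30 + √(0.148² + 0.119²) = 0.49.
- Fisher's exact p is 0.03.

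The overlapping intervals conceal a difference whose 95% interval excludes zero.

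**6. How much precision adjustment buys.** The documents give neither a baseline distribution nor a block size. Assume lognormal baseline (median 1.8 g/day, log SD 0.55, cut at 1 g/day), 40:20 allocation, and blocks of 3, 6 or 12 within stratum. The mean simulated difference is about 21 points. Its SD is 11.2-11.5 points unadjusted, 11.2-11.4 with Mantel-Haenszel stratification and 10.9-11.1 with logistic standardization on log baseline. From unrounded SDs, the gain in effective sample size is about 0-1% and about 6% (5-7% across runs).

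**7. What a test would deliver.** Assume instead baseline uniform on 1-2 and 2-5 g/day, a low-stratum share of 30%, 50% or 70%, and no dropout. At one-sided 0.05, a stratified CMH test of Partial Remission has power 45%, 51% or 59%, against 37%, 44% or 52% unstratified. With no effect, the stratified test rejects about 5% of the time and the unstratified test 3-4%.

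**The case against.** The strongest reply is that the plan is open and consistent. Protocol and SAP both call secondary analyses descriptive, Table 1 matches the text, and 60 participants per cohort in a proof-of-concept trial cannot support confirmatory responder claims. The primary analysis already gives a baseline- and stratum-adjusted effect with an interval on the same measurement. A crude risk difference can be computed from the tabulated counts, and nowhere does the SAP propose judging by overlap.

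Most of this stands, and it limits the point to a reporting gap. It does not remove it. An estimated difference with an interval is itself descriptive, and the same SAP already gives LN Week 50 proteinuria a between-arm ratio under that label. A crude difference rebuilt from counts ignores the stratified design and would be chosen after the data are seen.

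Two stronger readings are tempting. A reader might infer that ignoring baseline wastes the equivalent of about 13-14% (stratification) or 20% (standardization) of the patients. Those gains appear in the step 6 model only if allocation is not stratified; protocol 6.3.1 stratifies IgAN randomization on this variable, and the gains then nearly vanish. A reader might also infer that chance baseline imbalance could pass for a treatment effect. Stratification limits imbalance between strata, leaving only imbalance within them.

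**Conclusion.** The gap is real. The plan has no between-arm estimate for a key secondary IgAN endpoint or for the >30%/>50% responders, while comparable LN endpoints are tested between arms. Nothing in the SAP explains the difference.

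The consequence is moderate. No error rate is affected, no planned result is invalid, and the precision gain from adjustment is small. What is missing is a prespecified, valid interval for the difference the objective asks about. The baseline argument applies to Partial Remission alone. It rests on the plan's ratios and SD, plus normality and independence of log change from baseline; the precision and power figures also rest on assumed baseline distributions and, for precision, block sizes.

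The absence of an IgAN comparison at Week 50 should not be read as part of the gap. Placebo participants switch to ravulizumab at Week 26, so leaving that visit uncompared is right.

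**What to change.** Keep the per-arm percentages and exact intervals, and add:

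- **Main estimate.** A Mantel-Haenszel risk difference with 95% CI, stratified by each cohort's randomization factor: Σw(p₁ − p₀)/Σw with w = n₁n₀/(n₁ + n₀) in each stratum. Report it at Week 26 for Partial Remission (IgAN) and for the >30% and >50% responders (both cohorts), and at Week 50 for the >30% and >50% responders in LN only.
- **Supportive estimate for Partial Remission at Week 26.** A logistic model with treatment and log baseline proteinuria, standardized to a risk difference.
- **LN renal response.** The same stratified difference and CI beside the CMH tests for complete and overall renal response.
- **Table 1.** Change the summary measure to the difference in proportions for these endpoints and visits. Keep the per-arm proportion for IgAN at Week 50.
- **Label.** State that these are estimates without a multiplicity claim; the power in step 7 would not support more.

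The cost is SAP wording, one extra column per table and a short supportive model. No new data are needed.
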